9.1.2. Serious Adverse Event

An SAE is defined as an untoward medical occurrence that results in any of the following outcomes:

- Death (ie, all deaths occurring between signing of the consent form to within 30 days after last study drug administration), including deaths due to COVID-19 if no other event more satisfactorily explains the reason for death. Deaths that occur as a result of an AE that started during the study period should be reported. Death is not an SAE term; the reported AE should be the event that caused the death. Death is the outcome of this SAE.
- Life-threatening situation (ie, with an immediate risk of death from the event as it occurred but not including an event that, had it occurred in a more serious form, might have caused death).
- In-patient hospitalization or prolongation of existing hospitalization. Of note, an untoward medical occurrence that occurs during hospitalization is an AE but a complication that prolongs hospitalization is an SAE. In-subject hospitalization comprises formal admission to a hospital for medical reasons, for any length of time, whether or not hospitalization extends overnight. However, hospital admissions or prolongations of hospitalization for administration of the study drug or procedures required by the study protocol, diagnostic observations or procedures, administration of concomitant or subsequent therapy for the cancer, logistical issues (e.g. lengthy travel), or the convenience of the subject or clinical personnel are not considered serious.
- Persistent or significant disability/incapacity.
- Congenital anomaly/birth defect in the offspring of a subject who received the investigational medicinal product.
- Other medically significant event. Such events may not be immediately life-threatening or result in death or hospitalization, but based upon appropriate medical and scientific judgment, may jeopardize the subject, or may require medical or surgical intervention to prevent one of the outcomes listed above. Examples of such events might include:
 - Allergic bronchospasm requiring intensive treatment in an emergency room or at home
 - New cancers or blood dyscrasias
 - Convulsions that do not result in hospitalization
 - Development of drug dependency or drug abuse

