4.2.2. Clinical Efficacy

- The proportion of subjects treated with LAM-002A compared to placebo, who have disease progression by Day 28 as defined by the occurrence of:
 - \circ Hospitalization
 - o Death

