9. SAFETY ASSESSMENT

9.1. Definitions

9.1.1. Adverse Event

An AE is any untoward medical occurrence in a clinical investigation subject administered a medicinal product; the event does not necessarily have a causal relationship with study drug administration or usage. An AE can therefore be any unfavorable and unintended sign (including an abnormal laboratory finding), symptom, or disease temporally associated with the use of a medicinal product, whether or not considered related to the medicinal product.

In this study, any of the following events will be considered an AE:

- Any complication that occurs as a result of a protocol-mandated procedure (e.g. venipuncture, ECG).
- Any preexisting condition that increases in severity or changes in nature during or as a consequence of study drug administration. Worsening manifestations of the underlying infection (e.g. increase in COVID-19 manifestations) may be considered AEs in this study.
- Any injury or accident. If a medical condition is known to have caused the injury or accident (e.g. a fall secondary to dizziness), the medical condition (dizziness) and the accident (fall) should be reported as 2 separate AEs.
- Any abnormality in physiological testing or a physical examination finding that requires clinical intervention or further investigation (beyond ordering a repeat [confirmatory] test).
- Any laboratory (e.g. clinical chemistry, hematology, urinalysis) or investigational abnormality (e.g. ECG, X-ray) independent of the underlying medical condition that requires clinical intervention, results in further investigation (beyond ordering a repeat [confirmatory] test), or leads to investigational medicinal product interruption or discontinuation unless it is associated with an already reported clinical event. If the laboratory abnormality is part of a syndrome, the syndrome or diagnosis (e.g. anemia) not the laboratory result (e.g. decreased hemoglobin) should be recorded.
- A complication related to pregnancy or termination of a pregnancy (see Section 9.7.2 for additional information).

None of the following events is considered an AE:

- Laboratory abnormalities not requiring clinical intervention or further investigation. Such abnormalities will be captured as part of laboratory monitoring.

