12.4.4.1. Secondary Outcome: Hospitalization or Death Within 28 Days

The proportion of those progressing to hospitalization or death within 28 days of randomization will be compared between treatment groups using logistic regression (Ge 2011). All participants in the ITT population will be included in this analysis. Covariates in the analysis will include age. Site will be included as a random effect. The risk difference and 95% confidence interval will be estimated. Supportive analysis of this outcome will use the antiviral efficacy analysis population and the PP population.

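### Section 9.1.2 exempts observation admissions from seriousness without limiting this to planned stays, so an unplanned COVID-19 admission can be a progression event yet not meet the hospitalization criterion for an SAE

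*Combined protocol and SAP*

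**What the plan says.** Section 9.1.2 sets a broad rule first: hospitalization means "formal admission to a hospital for medical reasons, for any length of time, whether or not hospitalization extends overnight". The next sentence, introduced as an exception, takes several kinds of admission or prolongation back out. They are those for giving study drug or carrying out protocol procedures, those for "diagnostic observations or procedures, administration of concomitant or subsequent therapy for the cancer", those for logistical reasons, "or the convenience of the subject or clinical personnel are not considered serious".

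The same section has a separate route to SAE status for other medically significant events, which on medical judgment "may jeopardize the subject, or may require medical or surgical intervention to prevent one of the outcomes listed above". Section 9.1.1 says of the infection itself: "Worsening manifestations of the underlying infection (e.g. increase in COVID-19 manifestations) may be considered AEs in this study".

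On the efficacy side, Section 4.2.2 compares the proportions of subjects "who have disease progression by Day 28 as defined by the occurrence of" hospitalization or death. Section 12.4.4.1 analyses it in the ITT population: "The proportion of those progressing to hospitalization or death within 28 days of randomization". Table 1 footnote aa records the event at Day 28 as death, or hospitalization because of COVID-19. None of these three places excludes a stay because its purpose was observation or diagnosis.

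**The concern.** The trial treats outpatients with mild COVID-19, so an unplanned admission is a main way in which harm or lack of effect would show. Whether it is serious decides whether the site must report it to the sponsor within 24 hours (Section 9.7.1). It also decides whether the event enters the SUSAR assessment (Section 9.8) and the SAE summaries by arm (Section 12.4.8). An exemption for observation stays with no planned or elective limit leaves that decision to how a site words the reason for admission. Two sites could admit similar patients for the same reason, one filing an SAE and the other not, while both admissions count as progression.

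Section 2.3 notes that no subject with COVID-19 had yet received the drug and relies on the early DSMB review to catch unexpected risk. Uniform SAE classification matters more in that setting than it would for a drug already studied in this disease.

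**Working it through.** No arithmetic applies; the point rests on the wording of two definitions. The check takes four kinds of admission through both of them.

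| Admission | Progression event? | Meets the hospitalization criterion for seriousness? |
|---|---|---|
| A. Unplanned, to treat worsening COVID-19 | Yes | Yes: a formal admission for medical reasons, not on the exempt list |
| B. Unplanned, because of COVID-19, purpose given as observation or work-up | Yes: footnote aa asks about cause, not purpose or length | No, as written |
| C. Planned diagnostic procedure, unrelated to COVID-19 | No | No |
| D. For cancer therapy | No: not due to COVID-19 under footnote aa | No |

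The definitions disagree only for B.

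1. *Does the general rule rescue B?* No. The exemption is written as an exception to that rule, so it prevails where it applies.

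2. *Is the exemption limited elsewhere to planned stays?* No. Section 9.1.1 shows how such a limit can be written: it removes from the AE definition interventions with no untoward occurrence behind them, and gives elective surgery and social or convenience stays as examples. Section 9.1.2 puts no such condition on observation stays.

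3. *Is the endpoint limited so that B drops out of it?* No. Section 11.2.1 gives criteria for needing hospitalization (NEWS, respiratory failure, severe symptoms, ECOG status), and observation alone is not among them. But nothing says that only admissions meeting those criteria count as endpoint events.

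4. *Can B still become an SAE?* Yes, if it is judged life-threatening or medically significant. The second of these rests on judgment, and Section 9.1.1 permits but does not require that COVID-19 worsening be recorded as an AE. The outcome for B can therefore differ between sites.

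5. *Does the cancer clause matter?* It governs D, where the definitions agree. Exclusion criterion 7 already removes cancers likely to affect safety or interpretation, so the clause has no evident referent in this population.

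6. *Does the endpoint record fill the gap in time?* Only in part. Table 1 schedules the endpoint assessment at Day 28, while the first DSMB safety review is triggered when 15 subjects per arm have reached 11 days (Section 12.5). AE review does take place at the earlier visits.

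With the exemption limited to planned admissions that no untoward occurrence prompted, B becomes serious, A is unchanged, and C stays exempt if it was planned before consent. The definitions then agree on B.

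**The case against.** The strongest reply is that the exempt list should be read as a whole. Most of its items are stays with no untoward event behind them, and an SAE is by definition an untoward occurrence. On that reading a deteriorating patient is admitted for medical reasons and the exemption never applies. Section 11.2.1 supports this by tying the need for admission to severity, and the medically significant criterion is a further safeguard. This is a reasonable reading and probably the intended one, but the text does not state it. The observation item is undefined, and the safeguard depends on each site's judgment. The ambiguity stands.

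Several stronger conclusions that a reader might draw are not supported:

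- *That every observation admission would be lost as an SAE.* Other seriousness criteria can still apply.
- *That the whole exemption is an oncology remnant.* Only the cancer-therapy item is oncology wording; the observation item stands separately.
- *That the DSMB would not see these events.* Section 5.2 has it review AEs as well as SAEs, and gives it clinical efficacy as well as safety.
- *That a stopping rule or efficacy result would change.* Table 8 counts deaths only, and the Day 28 assessment captures the hospitalization whatever its SAE status.
- *That a large share of serious events is at stake.* The documents give no expected admission rate, SAE count or share of admissions for observation.

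SAE and efficacy definitions also serve different purposes, and nothing in the protocol requires their counts to match. The reason to change the text is consistent safety reporting, not equal totals.

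**Conclusion.** The point holds in a limited form. As written, Section 9.1.2 allows an unplanned COVID-19 admission for observation to be classed as non-serious under the hospitalization criterion while it counts as progression. The consequences are possible inconsistency between sites, possible loss of 24-hour reporting for some admissions, and SAE tallies that may omit admissions counted in the endpoint.

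No magnitude can be derived from the documents. The conclusion assumes that some sites would apply the exemption literally and would not invoke another seriousness criterion. If every site read it as covering only stays without an untoward event, there would be no mismatch. The correction is worth making because it is specific, costs almost nothing and improves safety reporting.

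**What to change.** In Section 9.1.2:

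- Limit the exemption to admissions planned before consent and not prompted by an untoward medical occurrence, or delete the diagnostic-observation item.
- Delete the cancer-therapy clause.
- State that an unplanned admission due to COVID-19 meets the hospitalization criterion for seriousness.

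A listing at database lock that compares endpoint hospitalizations with SAEs would be a useful check. Reconciling the two before each DSMB report is optional.

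The cost is a wording amendment and a few more SAE forms, plus one listing if the check is adopted. Treatment, endpoint, sample size and analysis are unchanged.

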9.1.3. Unexpected Adverse Event

An unexpected AE is defined as an event that has a nature, severity, or specificity that is not consistent with the applicable investigator brochure, or that is symptomatically and pathophysiologically related to a known toxicity but differs because of greater severity or specificity. For example, under this definition, hepatic necrosis would be unexpected (by virtue of greater severity) if the investigator brochure only referred to elevated hepatic enzymes or hepatitis. Similarly, cerebral thromboembolism and cerebral vasculitis would be unexpected (by virtue of greater specificity) if the investigator brochure only listed cerebral vascular accidents. "Unexpected," as used in this definition, refers to an adverse drug experience that has not been

previously observed and reported rather than an experience that has not been anticipated based on the pharmacological properties of the study drug.

9.1.4. Treatment-Emergent Adverse Event

A TEAE is defined as an AE that occurs or worsens in the period from the first dose of study drug administration to Day 28 of the study.

9.1.5. Adverse Events of Special Interest

There are no adverse events of special interest in this protocol.

9.2. Eliciting Adverse Event Information

The investigator is to report all directly observed AEs and all AEs spontaneously reported by the study subject. In addition, each study subject should be questioned about AEs at each scheduled study center visit or during any telephone contact with the subject. The type of question asked should typically be open-ended, e.g. "Have you had any new health problems?" or a similar type of query.

9.3. Recording Adverse Events

All AEs will be assessed by the investigator or qualified designee and recorded in the electronic case report forms (eCRFs). The following considerations apply in collecting AE information:

- Recognized medical terms (not colloquialisms, abbreviations, or jargon) should be used when recording AEs. Ideally the description should be consistent with MedDRA nomenclature.
- The medical diagnosis (ie, disease or syndrome) should be recorded instead of signs and symptoms (e.g. pneumonia instead of shortness of breath, coughing, and fever).
- Any sign or symptom considered as unrelated to an encountered disease or syndrome should be recorded as an individual AE (e.g. if nausea and severe headache are observed at the same time, each event should be recorded as a separate AE).
- If an AE resolves and reoccurs at a later date, a new AE must be documented and reported, as appropriate.

The following information should be recorded:

- Description as to whether the AE is serious, if applicable (see Section 9.1.2)
- The start date (date of AE onset)
- The stop date (date of AE resolution)
- The severity of the AE (see Section 9.4)
- A description of the relatedness of the AE to the study drug or to a study procedure (see Section 9.5)
- The action taken due to the AE
- The outcome of the AE

9.4. Grading of the Severity of an Adverse Event

The severity of AEs will be graded and reported using the CTCAE, Version 5.0.

If a CTCAE criterion does not exist, the investigator should use the grade or adjectives: Grade 1 (mild), Grade 2 (moderate), Grade 3 (severe), Grade 4 (life-threatening), or Grade 5 (fatal) to describe the maximum intensity of the AE. For purposes of consistency with the CTCAE, these intensity grades are defined in Table 3.

Grade	Adjective	Description			
Grade 1	Mild	Sign or symptom is present, but it is easily tolerated, is not expected to			
		have a clinically significant effect on the subject's overall health and			
		well-being, does not interfere with the subject's usual function, and is			
		not likely to require medical attention.			
Grade 2	Moderate	Sign or symptom causes interference with usual activity or affects			
		clinical status and may require medical intervention.			
Grade 3	Severe	Sign or symptom is incapacitating or significantly affects clinical status			
		and likely requires medical intervention and/or close follow-up.			
Grade 4	Life-threatening	Sign or symptom results in a potential threat to life.			
Grade 5	Fatal	Sign or symptom results in death.			

Table 3.Grading of Adverse Event Severity

The distinction between the seriousness and the severity of an AE should be noted. Severity is a measure of intensity; thus, a severe reaction is not necessarily a serious reaction. For example, a headache may be severe in intensity, but would not be classified as serious unless it met one of the criteria for serious events (as listed in Section 9.1.2).

9.5. Describing Adverse Event Relationship to Study Drug and Study Procedures

The investigator will evaluate the causal relationship of each AE to a study drug and/or to a study procedure (e.g. venipuncture or ECG evaluation) and record that relationship on the appropriate CRFs. Causality will be assessed considering whether the AE is reasonably related to the study drug or procedure or whether the AE is not reasonably related to the study drug or procedure considering the definitions in Table 4.

It should be emphasized that the determination of the relationship of an adverse event to study drug (LAM-002A or placebo) should be based on the presumption that the study subject is receiving active LAM-002A even though the blind remains unbroken. As noted in Section 8.3, unblinding should be avoided unless absolutely necessary for a subject's well-being; breaking the blind should not be performed merely to obtain enhanced certainty regarding the relationship of an adverse event to study drug.

Relationship	Description				
Definite	A clinical event in which a relationship to the use of the study drug seems definite because of such factors as consistency with known effects of the drug; a clear temporal association with the use of the drug; lack of alternative explanations for the event; improvement upon withdrawal of the drug (de-challenge); and recurrence upon resumption of the drug (rechallenge).				
Probable	A clinical event in which a relationship to the study drug seems probable because of such factors as consistency with known effects of the drug; a reasonable temporal association with the use of the drug; lack of alternative explanations for the event; and improvement upon withdrawal of the drug (de-challenge).				
Possible	A clinical event with a reasonable temporal association with administration of the study drug, and that is not likely to be explained by concurrent disease or other drugs or chemicals. Information on drug withdrawal may be lacking.				
Unlikely	A clinical event with a temporal relationship to study drug administration that makes a causal relationship improbable and for which other factors suggesting an alternative etiology exist. Such factors might include a known relationship of the clinical event to a concomitant drug, past medical history of a similar event, the subject's disease state, intercurrent illness, or environmental factors.				
Unrelated	A clinical event in which a relationship to the study drug seems improbable because of factors such as inconsistency with known effects of the study drug; lack of a temporal association with study drug administration; lack of association of the event with study drug withdrawal or rechallenge; and/or presence of alternative explanations for the event. Alternative explanations might include a known relationship of the clinical event to a concomitant drug, past medical history of a similar event, the subject's disease state, intercurrent illness, or environmental factors.				

Table 4.Relationship of Study Drug to Adverse Event

9.6. Adverse Event Reporting Period

The start of the AE reporting for a study subject will coincide with the first administration of study drug for this study. After the first administration of study drug, all AEs (serious and nonserious, related and unrelated) should be reported. Unless a subject withdraws consent for follow-up, each subject must be followed until the end of the AE reporting period at Day 28 or when any ongoing drug-related AEs and/or SAEs have resolved or become stable. The investigator should use appropriate judgment in ordering additional tests as necessary to monitor the resolution of events. The medical monitor or the sponsor may request that certain AEs be followed longer.

Investigators are not obligated to actively seek information regarding the occurrence of new SAEs beginning after Day 28. However, if the investigator learns of such an SAE and that event is deemed relevant to the use of LAM-002A, he/she should promptly document and report the event. A longer reporting period applies in the case of pregnancy (see Section 9.7.2).

9.7. Study Center Reporting Requirements

9.7.1. Adverse Event Reporting Requirements

Classification of an event as serious or nonserious (see Section 9.1) determines the reporting procedures to be followed by the study center. Study center reporting requirements for AEs are summarized in Table 5.

Classification	Reporting Time	Reporting Action		
Serious	Within 24 hours of becoming aware	E-mail report on designated SAE report form to		
	of the event	the sponsor or designee [a] and to the study center		
		IRB, as per local IRB/IEC requirements		
	Within 10 working days	E-mail copies of relevant source documents (e.g.		
		progress notes, laboratory and diagnostic test		
		results, discharge summaries) [b] to the sponsor or		
		designee [a].		
	Per eCRF submission procedure	Record and submit information on appropriate		
		eCRFs.		
Nonserious	Per eCRF submission procedure	Record and submit information on appropriate		
		eCRFs.		

 Table 5.
 Study Center Reporting Requirements for Adverse Events

a. See contact information provided.

b. Subject name, address, and other personal identifiers should be obscured but without losing the traceability of a document to the study subject identifiers.

Abbreviations: eCRF=case report form; IRB/IEC= institutional review board/independent ethics committee; SAE=serious adverse event

For SAEs, in addition to completing the AE portion of the eCRF, an SAE report form must also be completed and emailed within 24 hours of first awareness of the event to the sponsor (or designee).

Investigators must also submit written safety reports as required by the IRB/IEC within timelines set by local and regional regulations. The study site should retain documentation of the submission of expedited safety reports to the IRB/IEC, and their receipt. Study site personnel should not wait to receive complete information or the investigator's signature before notifying the sponsor (or designee) and the IRB/IEC of an SAE.

The following minimum information is required:

- Subject identification (i.e. subject number, sex, age)
- Description of the SAE (diagnosis preferred, symptoms, etc.)
- Study drug and causal relationship of the SAE to the study drugs or study procedures
- Investigator name

Collection of complete information concerning SAEs is extremely important. The information in the AE portion of the eCRF and the SAE report form must match or be reconciled. Where the same data are collected, the forms must be completed in a consistent manner. For example, the same AE term should be used on both forms.

All available and relevant supporting documentation (e.g. progress notes, pertinent laboratory and diagnostic test results, discharge summaries) should also be provided. The subject's name, address, and other personal identity information should be obscured on any source documents (e.g. progress notes, nurses' notes, laboratory and diagnostic test results, discharge summaries). The subject's unique study number should be included on each page of any document provided.

The sponsor (or designee) will review SAE reports for missing information and send queries to the site for resolution as indicated. The study site is responsible for obtaining pertinent follow-up information missing from initial reports and forwarding the information within 24 hours of

receipt to the sponsor (or designee). Follow-up information to the SAE should be clearly documented as "follow-up" in the SAE report form.

The original SAE form and any follow-up forms must be kept on file at the study site. An SAE is followed until it is considered resolved, it returns to baseline, is chronically ongoing, or explained otherwise by the principal investigator.

